#### Adequate organ function: 8.

System	Laboratory Value
Hematological	
Absolute neutrophil count	≥1500/µL
Platelets	≥100 000/µL
Hemoglobin	≥9.0 g/dL or ≥5.6 mmol/L a
Renal	
Creatinine OR Measured or calculated b creatinine clearance (GFR can also be used in place of creatinine or CrCl)	≤1.5 × ULN OR ≥30 mL/min for patient with creatinine levels >1.5 × institutional ULN
Hepatic	
Total bilirubin	≤1.5 × ULN OR direct bilirubin ≤ULN for patients with total bilirubin levels >1.5 × ULN
AST (SGOT) and ALT (SGPT)	$\leq$ 2.5 × ULN ( $\leq$ 5 × ULN for patients with liver metastases)
Coagulation	
International normalized ratio OR PT aPTT	≤1.5 × ULN unless patient is receiving anticoagulant therapy as long as PT or aPTT is within therapeutic range of intended use of anticoagulants
ALT (SGPT)=alanine aminotransferase (serum glutamic pyruvic transaminase); aPTT=activated partial thromboplastin time; AST (SGOT)=aspartate aminotransferase (serum glutamic ovaloacetic transaminase); CrCL=creatinine clearance; GFR=glomerular	

(serum glutamic oxaloacetic transaminase); CrCL=creatinine clearance; GFR=glomerular filtration rate; PT=prothrombin time; ULN=upper limit of normal.

- a Hematology test should be obtained without transfusion or receipt of stimulating factors within 2 weeks before obtaining screening blood sample.
- b CrCl should be calculated per institutional standard.
  - 9. Patient (or legally acceptable representative if applicable) provides written informed consent for the study.

#### **6.2. Exclusion Criteria**

- Patients with limited cSCC, who do not require systemic therapy 1.
- Has known active central nervous system metastases and/or carcinomatous meningitis. Patients with previously treated brain metastases may participate provided they are radiologically stable, i.e., without evidence of progression for ≥4 weeks by repeat imaging (note that the repeat imaging should be performed during study screening),

- clinically stable and without requirement of steroid treatment for  $\geq$ 14 days prior to first dose of study treatment.
- 3. Has a diagnosis of immunodeficiency or autoimmune disease, or is receiving chronic systemic steroid therapy (in dosing exceeding 10 mg daily of prednisone equivalent) or any other form of immunosuppressive therapy within 3 weeks prior the first dose of study treatment
- 4. Patients who have a history of (non-infectious) pneumonitis that required steroids or have current pneumonitis
- 5. Has received prior therapy with an anti-PD-1, anti-PD-L1, or anti-PD-L2 agent, or with an agent directed to another stimulatory or co-inhibitory T cell receptor (e.g., cytotoxic T-lymphocyte-associated antigen 4, OX 40, CD137) and was discontinued from that treatment due to a >Grade 3 irAE
- 6. Has severe hypersensitivity (≥Grade 3) to pembrolizumab or IFX-1 and/or any of their excipients or had a severe (≥Grade 3) infusion-related reaction to treatments with other mAbs
- 7. Patients who fulfil inclusion criterion 6 (washout times) but who have not recovered from side effects of such therapies

Note: Patients must have recovered from all AEs due to previous therapies to ≤Grade 1 or baseline. Patients with ≤Grade 2 neuropathy may be eligible. If patients received major surgery, they must have recovered adequately from the toxicity and/or complications from the intervention prior to starting study treatment.

- 8. Has received a live vaccine within 30 days prior to the first dose of study treatment (see Section 7.4.1)
- 9. Patients who have undergone major surgery <4 weeks prior to starting study treatment
- 10. Is currently participating in or has participated in a study of an investigational agent or has used an investigational device within 4 weeks prior to the first dose of study treatment

Note: Patients who have entered the follow-up phase of an investigational study may participate as long as it has been 4 weeks after the last dose of the previous investigational agent.

- 11. Patients with known ≥Grade 3 (per NCI CTCAE v5.0 criteria) active systemic or cutaneous viral, bacterial, or fungal infection
- 12. Patients with known history of Hepatitis B or C infections or known to be positive for Hepatitis B antigen (HBsAg)/ Hepatitis B virus (HBV) DNA or Hepatitis C Antibody or RNA. Active Hepatitis C is defined by a known positive Hep C Ab result and known quantitative HCV RNA results greater than the lower limits of detection of the assay.
- 13. Patients who have a history of human immunodeficiency virus infection
- 14. Patients who have a history of interstitial lung disease
- 15. Patients who have had an allogeneic tissue/solid organ transplant
- 16. Patients with a history of other malignancies during the past 5 years.

Note: The following are exempt from the 5-year limit: curatively resected basal cell carcinoma, or carcinoma in situ (e.g., breast carcinoma, cervical cancer in situ) that have undergone potentially curative therapy.

- 17. Patients who are pregnant or breastfeeding or expecting to conceive or father children within the projected duration of the study, starting with the screening visit through after the last dose of IFX-1 or 120 days after the last dose of pembrolizumab
- 18. Women of childbearing potential (WOCBP) who have a positive serum pregnancy test result within 7 days before treatment

Note: Post-menopausal women must be amenorrheic for  $\geq 12$  months to be considered not WOCBP (Appendix 7).

- 19. Male patients and WOCBP who do not agree to practice an effective method of contraception during study and after last dose of IFX-1 or 120 days after last dose of pembrolizumab (Appendix 7)
- 20. Patients with congestive heart failure, Class III or IV, by New York Heart Association criteria
- 21. Patients with any serious underlying medical condition that would impair their ability to receive or tolerate the planned treatment
- 22. Patients with dementia or altered mental status that would preclude understanding and rendering of informed consent document

# **6.3.** Screening Failures

Screening failures are defined as patients who are enrolled (i.e., consent to participate) in the clinical study but are not subsequently assigned to study treatment. A set of screen failure information will be collected and include demography, eligibility criteria, AE, and reason for screening failure.

Individuals who do not meet the criteria for participation in this study (screening failure) may be rescreened if failed eligibility criteria can only be corrected outside the first screening period.

# **6.4.** Meals and Dietary Restrictions

Patients should maintain a normal diet unless modifications are required to manage an AE such as diarrhea, nausea, or vomiting.

# 7. STUDY DRUG(S) AND ADMINISTRATION

# 7.1. Investigational Medicinal Product

IMP is defined as any investigational treatment(s), marketed product(s), placebo, or medical device(s) intended to be administered to a study patient according to the study protocol.

# 7.1.1. IFX-1

# 7.1.1.1. Packaging and Labelling of Investigational Medicinal Product

IFX-1 concentrate for solution for infusion will be supplied in mL glass vials at a concentration of mg/mL (mg mg per vial) for reconstitution and intravenous administration. Apart from IFX-1, the solution will contain sodium chloride, sodium phosphate, and polysorbate 80.

IFX-1 will be packaged in cartons and labeled in accordance with all legal requirements.

Each carton (or IMP kit) will be labeled with a unique number (IMP kit number). The glass vials containing IFX-1 will be labeled with the same medication number as the cartons in which they are packed.

Each carton and each vial will be labeled with a multilingual booklet label or a country specific single panel label as applicable.

# 7.1.1.2. Storage, Handling, and Accountability

Vials of IFX-1 must be stored

. All supplies of IFX-1 must be stored separately or segregated from other study supplies and site stock in a dedicated locked facility with access limited to authorized personnel. All storage facilities must be temperature controlled and monitored and compliant with applicable regulatory requirements.

An established and validated local temperature management system with temperature logs should be used to record the storage temperature. If this is not possible, the study site will be provided with a temperature record form by the Contract Research Organization and the site personnel will maintain temperature records for the entire duration of the study. At a minimum, the daily (working day) minimum and maximum temperatures must be documented.

Any deviation from the specified temperature range must be documented and reported within 24 hours (or the next working day). Further instruction on the management and reporting of temperature deviations is provided in the Pharmacy Manual.

The investigator or designee must confirm appropriate temperature conditions have been maintained during shipment for all IMP received and any discrepancies are reported and resolved before use of the IMP.

Only patients enrolled in the study may receive IMP and only authorized site staff may prepare and administer IMP. The IMP must be prepared in a controlled area in accordance with local regulations/requirements for reconstitution of products for intravenous administration; see Pharmacy Manual for more details.

The investigator, institution, or the head of the medical institution (where applicable) is responsible for the correct storage of IMP, IMP accountability, reconciliation, and record maintenance (i.e., receipt, reconciliation, and final disposition records).

Further guidance and information for the final disposition of unused IMP are provided in the Pharmacy Manual.

# 7.1.1.3. Drug Preparation and Administration Instructions

The IFX-1 for infusion will be reconstituted (prepared) in a controlled area at the study site or at the study site's pharmacy, in accordance (compliance) with applicable local regulations/requirements for reconstitution of products for intravenous administration.

The reconstituted IFX-1 should be used within hours after dilution when stored at room temperature. Otherwise, the reconstituted IFX-1 has to be stored at and used within 24 hours; if the reconstituted IFX-1 solution is stored in a refrigerator, it must be left to acclimatize to room temperature prior to administration. Details on reconstituting the IFX-1 will be provided in the Pharmacy Manual.

The number of unused, partially used, and empty vials will be documented accurately, and the vials will be kept at the site until the drug accountability documentation has been checked by the study monitor.

Any unused medicinal product or waste material should be disposed of in accordance with local requirements.

# 7.1.1.4. Recall of Investigational Medicinal Product

Instructions (actions to be taken by site) in the case of IMP recall will be provided in the Pharmacy Manual.

#### 7.1.2. Pembrolizumab

# 7.1.2.1. Packaging and Labelling of Investigational Medicinal Product

Pembrolizumab, 25 mg/mL concentrate for solution for infusion will be supplied as described in the Pharmacy Manual.

# 7.1.2.2. Storage, Handling, and Accountability

Storage conditions for pembrolizumab are described in the Pharmacy Manual.

An established and validated local temperature management system with temperature logs should be used to record the storage temperature. If this is not possible, the study site will be provided with a temperature record form by the Contract Research Organization and the site personnel will maintain temperature records for the entire duration of the study. At a minimum, the daily (working day) minimum and maximum temperatures must be documented.

Any deviation from the specified temperature range must be documented and reported within 24 hours (or the next working day). Further instruction on the management and reporting of temperature deviations is provided in the Pharmacy Manual.

The investigator or designee must confirm appropriate temperature conditions have been maintained during shipment for all IMP received and any discrepancies reported and resolved before use of the IMP.

Only patients enrolled in the study may receive IMP and only authorized site staff may prepare and administer IMP. The IMP must be prepared in a controlled area in accordance with local regulations/requirements for reconstitution of products for intravenous administration

The investigator, institution, or the head of the medical institution (where applicable) is responsible for the correct storage of IMP, IMP accountability, reconciliation, and record maintenance (i.e., receipt, reconciliation, and final disposition records).

Further guidance and information for the final disposition of unused IMP are provided in the Pharmacy Manual.

# 7.1.2.3. Drug Preparation and Administration Instructions

The pembrolizumab for infusion will be reconstituted (prepared) in a controlled area at the study site or at the study site's pharmacy, in accordance (compliance) with applicable local regulations/ requirements for reconstitution of products for intravenous administration. Details on preparation and administration of pembrolizumab will be provided in the Pharmacy Manual.

The number of unused, partially used, and empty vials will be documented accurately, and the vials will be kept at the site until the drug accountability documentation has been checked by the study monitor.

Any unused medicinal product or waste material should be disposed of in accordance with local requirements.

# 7.1.2.4. Recall of Investigational Medicinal Product

Instructions (actions to be taken by site) in the case of IMP recall will be provided in the Pharmacy Manual.

# 7.2. Administration and Dosage

Patients will be openly assigned to either receive IFX-1 as monotherapy in treatment Arm A or IFX-1 in combination with pembrolizumab in treatment Arm B. IFX-1 will generally be administered 60 minutes (±10 minutes) post administration of pembrolizumab.

The first dose of IFX-1 is administered at Cycle 1 Day 1. The first dose of pembrolizumab is administered at Cycle 1 Day 8. Subsequent doses of IFX-1 and pembrolizumab may be administered up to 1 day before or after the scheduled day within the Cycle 1 and up to 3 days before or after the scheduled day of all following cycles due to administrative reasons.

To allow for a close observation of study treatment infusion(s), patients should remain at the study site for  $\geq$ 60 minutes after end of infusion(s). Appropriate treatment for potential infusion-related reactions must be available during this time.

#### 7.2.1. Treatment Administered

# 7.2.1.1. Monotherapy Arm A

IFX-1 monotherapy will be administered as a 30-minute (-5/+10 minutes) intravenous infusion. Because of the variability of infusion pumps from site to site, a window between -5 minutes and +10 minutes is allowed. Administrations will be given as follows (Figure 2):

- Cycle 1 Days 1, 4, 8, and 15: 800 mg IFX-1 (4 administrations).
- From Cycle 1 Day 22 on: 1600 mg IFX-1 Q2W until EOT (two administrations during Cycle 1 on Days 22 and 36 and 3 administrations per cycle on Days 1, 15, and 29 of Cycle 2 and all subsequent cycles).

Cycle 1 will comprise 7 weeks, whereas all following cycles will comprise 6 weeks of treatment.

Treatment will be continued until either disease progression is diagnosed, unacceptable toxicity occurred, or treatment has been administered for approximately 2 years.

[figure not shown]

Figure 2 Patient Calendar: Arm A (IFX-1 Monotherapy)

C: cycle; D: day; IC: informed consent; PD: progressive disease; Q2W: bi-weekly; Q6W: every 6 weeks; TA: tumor assessment.

# 7.2.1.2. Combination Therapy Arm B

As detailed in Section 5.1, Stage 1 of treatment Arm B consists of a safety run-in with patients being sequentially assigned to 1 out of 3 different escalating treatment regimens (Figure 3).

IFX-1 will be administered as a 30-minute (-5/+10 minutes) intravenous infusion as follows:

- Cycle 1: 400 mg (regimen 1), 600 mg (regimen 2), or 800 mg (regimen 3) IFX-1 (4 administrations on Days 1, 4, 8, and 15)
- From Cycle 1 Day 22 on:800 mg IFX-1 Q2W (regimen 1), 1200 mg IFX-1 Q2W (regimen 2), or 1600 mg IFX-1 Q2W (regimen 3) until EOT (2 administrations during Cycle 1 on Days 22 and 36 and 3 administrations per cycle on Days 1, 15, and 29 of Cycle 2 and all subsequent cycles)

IFX-1 treatment will be combined with pembrolizumab, starting at Cycle 1 Day 8 and then on Day 1 of each treatment cycle after all other procedures and assessments have been completed. IFX-1 infusion will start 60 minutes (±10 minutes) after the pembrolizumab infusion has been finished.

For those patients receiving less than 1600 mg IFX-1 Q2W (regimen 1 and 2) the dose of IFX-1 may be increased to 1600 mg Q2W at the discretion of the investigator after consultation of the sponsor as soon as the safety of this dose will have been confirmed in at least 3 patients receiving 1600 mg Q2W (regimen 3). This intrapatient dose escalation will only be allowed provided that patient has received at least 2 cycles of IFX-1 and had no Grade  $\geq$  2 treatment related adverse events.

Pembrolizumab will be administered as a 30-minute (-5/+10 minutes) intravenous infusion at a dose of 400 mg Q6W. Sites should make every effort to target infusion timing to be as close to 30 minutes as possible.

The Pharmacy Manual contains specific instructions for the preparation of the pembrolizumab infusion and administration of infusion solution.

Treatment will continue until PD/iCPD or treatment discontinuation for any other reason (see Section 7.2.4) or treatment has been administered for approximately 2 years. If treatment will discontinue due to toxicity, continuation of either IFX-1 or pembrolizumab is allowed, given that the toxicity can be unequivocally attributed to 1 of the drugs (see Section 7.2.4.2).

Regimen 2: Regimen 1: Regimen 3: IFX-1 (400 mg) IFX-1 (600 mg) IFX-1 (800 mg) Pembrolizumab (400 mg) Pembrolizumab (400 mg) Pembrolizumab (400 mg) IFX-1 (800 mg) IFX-1 (1200 mg) IFX-1 (1600 mg) IFX-1: Q2W + Pembro: Q6W until PD Follow-up Screening Treatment IC Cycle C1 C1 C2 C2 C2 C4 C1 C3 Disease Day D1,4,8 D15 D22 D36 D1 D15 D29 D1 D1 Progression Tumor TA: O6W

Figure 3 Patient Calendar: Combination Arm B (IFX-1 + Pembrolizumab)

C: cycle; D: day; IC: informed consent; PD: progressive disease; Q2W: bi-weekly; Q6W: every 6 weeks; TA: tumor assessment.

#### 7.2.2. Treatment Modification

This protocol allows some alteration from the currently outlined dosing schedule, but a dose reduction of study treatment is generally not allowed. Patients treated in the safety run-in part of Arm B will be allowed to increase the assigned IFX-1 dose when the next higher dosing regimen was found to be safe by the steering committee (see Section 5.3.2). Increase to a higher than the planned highest dose, i.e., 800 mg QW as part of the fractionated loading dose on Cycle 1 Days 1, 4, 8, and 15 or 1600 mg Q2W from Cycle 1 Day 22 on, is not allowed and would require a protocol amendment.

All AEs leading to treatment modifications will be graded using NCI CTCAE v5.0 based on the investigator's assessment.

 more patients will be enrolled at the identified MTD or highest IFX-1 dose level (Regimen 3) in case only 3 patients have been previously treated in this dose cohort before it can be finally selected for Stage 2.

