# 5.3.2. Combination Therapy Arm B

In Arm B, during the safety run-in for each combination regimen cohort, the first 2 patients must be enrolled sequentially separated by a minimum of one week.

At the following time points, the Committee will review patient safety:

- For the very first patient receiving the combination therapy: After Cycle 1, Day 36, when this patient will have received the four consecutive IFX-1 fractionated loading dose administrations, one pembrolizumab administration, and two of the higher IFX-1 Q2W doses (to allow inclusion of subsequent patients)
- For each escalating dosing regimen: After 3 patients of each combination regimen cohort will have reached Cycle 1, day 36, at which they will have received the four consecutive IFX-1 fractionated loading dose administrations, one pembrolizumab administration, and two of the higher IFX-1 Q2W doses (to determine occurrence of DLT and necessity to include 3 more patients in a given dose cohort, to allow treatment in the next higher dose cohort, or to determine the MTD or RP2D)

To determine the RP2D, 6 patients should be treated at the MTD or highest dose level. If only 3 patients will have been enrolled into the respective cohort, 3 more patients will be enrolled at the same dose level. If no further toxicities are observed, this MTD will be selected as dose for Stage 2 and recommended combination regimen. Further patient enrollment in Arm B can proceed without specific rules.

The steering committee will continue to meet every three months until the last patient will have completed the third month of treatment in Stage 1 of the study and every six months thereafter to further confirm safety of the MTD or RP2D, and to further assess general safety of study treatment administration. All available safety data will be provided to the steering committee before each meeting.

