# **7.2.2.2.1.** Immune-Related Adverse Events

AEs associated with pembrolizumab exposure may represent an immune-related response. These irAEs may occur shortly after the first dose or several months after the last dose of pembrolizumab treatment and may affect more than one body system simultaneously. Therefore, early recognition and initiation of treatment is critical to reduce complications. Based on existing clinical study data, most irAEs were reversible and could be managed with interruptions of pembrolizumab, administration of corticosteroids, and/or other supportive care. For suspected irAEs, ensure adequate evaluation to confirm etiology or exclude other causes. Additional procedures or tests such as bronchoscopy, endoscopy, and skin biopsy may be included as part of the evaluation. Dose modification criteria for pembrolizumab in response to Grade 2 or higher irAEs are listed in

Appendix 8, Table 4. If treatment should be withheld due to toxicity, both pembrolizumab and IFX-1 should be withheld (see Appendix 8, Table 4).

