# 7.2.3. Re-Dosing Criteria

The following criteria must be fulfilled to allow for re-dosing of study treatment:

- Absence of treatment discontinuation criteria (see Section 7.2.4)
- AEs fulfilling DLT criteria (see Section 7.2.2.2.3) must have been reviewed by the steering committee (see Section 5.3.2) and found not to be limiting.
- Any other Grade 3 or higher AEs have to improve to Grade 1 or baseline OR a Grade 3 AE can be managed and stabilized by supportive/medical therapy, e.g., Grade 3 hypertension can be controlled by addition of a second antihypertensive medication and should improve to Grade 1 or baseline.

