Type 1 diabetes mellitus (T1DM) or hyperglycemia	New onset T1DM or Grade 3 or 4 hyperglycemia associated with evidence of β-cell failure	Withhold d	
 
Initiate insulin replacement therapy for patients with T1DM
 
Administer antihyperglycemic in patients with hyperglycemia
 
	Monitor patients for hyperglycemia or other signs and symptoms of diabetes	
Hypophysitis	Grade 2 Grade 3 or 4	Withhold Withhold or permanently discontinue d	Administer corticosteroids and initiate hormonal replacements as clinically indicated	Monitor for signs and symptoms of hypophysitis (including hypopituitarism and adrenal insufficiency)	
Hyperthyroidis m	Grade 2 Grade 3 or 4	Continue  Withhold or	Treat with nonselective beta-blockers (e.g., propranolol) or thionamides as	Monitor for signs and symptoms of thyroid disorders	
		permanently discontinue d	appropriate		
Hypothyroidism	Grade 2, 3, or 4	Continue	Initiate thyroid replacement hormones (e.g., levothyroxine or liothyronine) per standard of care	Monitor for signs and symptoms of thyroid disorders	
Nephritis: grading	Grade 2	Withhold	Administer corticosteroids	Monitor changes of renal function	
according to increased creatinine or acute kidney injury	Grade 3 or 4	Permanently discontinue	(prednisone 1 to 2 mg/kg or equivalent) followed by taper		
Neurological	Grade 2 Grade 3 or 4	Withhold Permanently	Based on severity of AE administer corticosteroids	Ensure adequate evaluation to confirm etiology and/or	
Toxicities		discontinue		exclude other causes	
Myocarditis	Grade 2, 3 or 4	Permanently discontinue	Based on severity of AE administer corticosteroids	Ensure adequate evaluation to confirm etiology and/or exclude other causes	
Exfoliative	Suspected SJS, TEN, or DRESS	Withhold	Based on severity of AE administer corticosteroids	Ensure adequate evaluation to confirm etiology or exclude other causes	
Dermatologic Conditions	Confirmed SJS, TEN, or DRESS	Permanently discontinue			
All Other in A E-	Persistent Grade 2	Withhold or	Based on severity of AE administer corticosteroids	Ensure adequate evaluation to confirm etiology or exclude other causes	
All Other irAEs	Grade 3	Withhold or discontinue based on the event e		eactude oniet causes	

Recurrent	Permanently	
Grade 3 or	discontinue	
Grade 4		

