#### Note: Non-irAE will be managed as appropriate, following clinical practice recommendations.

- a AST/ALT: >3.0  $5.0 \times$  ULN if baseline normal; >3.0  $5.0 \times$  baseline, if baseline abnormal; bilirubin: >1.5  $3.0 \times$  ULN if baseline normal; >1.5  $3.0 \times$  baseline if baseline abnormal
- b AST/ALT: >5.0 20.0 × ULN, if baseline normal; >5.0 20.0 × baseline, if baseline abnormal; bilirubin: >3.0 10.0 × ULN if baseline normal; >3.0 10.0 × baseline if baseline abnormal
- c AST/ALT: >20.0 × ULN, if baseline normal; >20.0 × baseline, if baseline abnormal; bilirubin: >10.0 × ULN if baseline normal; >10.0 × baseline if baseline abnormal
- d The decision to withhold or permanently discontinue pembrolizumab and/or IFX-1 is at the discretion of the investigator or treating physician. If control achieved or ≤Grade 2, pembrolizumab and/or IFX-1 may be resumed.
- e Events that require discontinuation include but are not limited to: encephalitis and other clinically important irAEs (eg. vasculitis and sclerosing cholangitis).

Table 5 Dose Modification and Toxicity Management Guidelines for Infusion-Related Reactions Associated with Pembrolizumab or IFX-1

NCI CTCAE Grade  Grade 1  Mild reaction; infusion interruption not indicated; intervention not indicated Grade 2  Requires therapy or infusion interruption but responds promptly to symptomatic treatment	
 
Treatment
 
Increase monitoring of vital signs as medically indicated until the patient is deemed medically stable in the opinion of the investigator.
 
Stop Infusion.
 
Additional appropriate medical therapy may include
 
	None  Patient may be
Mild reaction; infusion interruption not indicated; intervention not indicated  Grade 2  Requires therapy or infusion interruption but responds promptly to	
 
indicated until the patient is deemed medically stable in the opinion of the investigator.
 
Stop Infusion.
 
	
Grade 2 Requires therapy or infusion interruption but responds promptly to	=	Patient may be

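### Section 7.2.2 permits an IFX-1 step from 800 to 1200 mg Q2W without the patient-level safety conditions that Section 7.2.1.2 sets for intrapatient escalation

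*Combined protocol and SAP*

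**What the plan says.** Two sections of the protocol govern increases of IFX-1 within a patient in Arm B.

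- **Section 7.2.2 (Treatment Modification).** Run-in patients will be "allowed to increase the assigned IFX-1 dose when the next higher dosing regimen was found to be safe by the steering committee". The only cross-reference is to Section 5.3.2. No increase may go beyond the highest planned dose (800 mg loading, 1600 mg Q2W).
- **Section 7.2.1.2 (Combination Therapy Arm B).** A patient on regimen 1 or 2 may go to 1600 mg Q2W at the investigator's discretion, after the sponsor has been consulted and once 1600 mg has been confirmed safe in at least 3 regimen 3 patients. It then adds: "This intrapatient dose escalation will only be allowed provided that patient has received at least 2 cycles of IFX-1". The same sentence also requires that the patient had no treatment-related AE of Grade 2 or higher.

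Section 5.3.2 schedules the committee's review for each regimen "After 3 patients of each combination regimen cohort will have reached Cycle 1, day 36". It contains no rule about raising an individual patient's dose. The synopsis repeats the 1600 mg rule with sponsor consultation but leaves out the 2-cycle and Grade 2 conditions.

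**The concern.** In 7.2.1.2 the sponsor decided that a patient with a related AE of Grade 2 or higher should not go to a higher dose. Section 7.2.2 opens a route to a higher dose that does not carry that decision, and neither section refers to the other. A site following 7.2.2 could move a regimen 1 patient to 1200 mg Q2W on the committee's cohort finding alone. A site following 7.2.1.2 would find no such step.

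Entry to the higher dose matters because 7.2.2 also says that dose reduction is generally not allowed. If a patient escalated in this way does badly, the usual remedy is to hold or stop the drug, not to step back. Section 9.7.1 notes that this is the first IFX-1 study in a malignant disease.

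**Working it through.** **1. The two rules side by side**

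| | 7.2.2 | 7.2.1.2 |
|---|---|---|
| Dose reached | Next higher regimen, up to 1600 mg Q2W | 1600 mg Q2W only |
| Cohort trigger | Committee finds the next regimen safe | 1600 mg confirmed safe in at least 3 regimen 3 patients |
| Sponsor consulted | Not stated | Required |
| Minimum exposure | Not stated | At least 2 cycles |
| Related AE history | Not stated | No Grade 2 or higher |

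**2. Which steps are in conflict.** The Q2W doses are 800, 1200 and 1600 mg for regimens 1, 2 and 3.

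- Regimen 2 to 3 (1600/1200 = 1.33, +33%): covered by both sections. The restrictive wording of 7.2.1.2 still applies.
- Regimen 1 straight to 1600 mg (1600/800 = 2.00, +100%): covered by 7.2.1.2 with its conditions.
- Regimen 1 to 2 (1200/800 = 1.50, +50%): permitted by 7.2.2 and absent from 7.2.1.2. The escalation that 7.2.1.2 makes conditional is the rise to 1600 mg described just before, so its conditions do not reach this step.

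**3. Can a patient with a Grade 2 related AE still be on drug?** Appendix 8, Table 4 withholds or stops treatment for most Grade 2 irAEs, and under Section 7.2.2.2.1 "If treatment should be withheld due to toxicity, both pembrolizumab and IFX-1 should be withheld". Four situations remain:

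- Grade 2 hypothyroidism: Table 4 says to continue both drugs and "Initiate thyroid replacement hormones (e.g., levothyroxine or liothyronine) per standard of care".
- A first Grade 2 infusion reaction: Table 5 allows a restart at half the rate if symptoms resolve within 1 hour, and Section 7.3 lets patients with mild or moderate reactions continue.
- A non-immune Grade 2 AE: "Non-irAE will be managed as appropriate, following clinical practice recommendations". The re-dosing rule in Section 7.2.3 does not stop it, because beyond DLT-type events it addresses only higher grades: "Any other Grade 3 or higher AEs have to improve to Grade 1 or baseline".
- A resolved Grade 2 irAE: general instruction 4 of Table 4 allows dosing to resume at Grade 1 or lower after the steroid taper. The AE history would still bar escalation under 7.2.1.2.

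**4. Patients.** Section 5.4 plans 3 to 6 patients per regimen. If regimen 2 is not cleared, 0 patients are affected. If it is cleared, the ceiling is 1 regimen × 3 to 6 = 3 to 6 patients, counting only those still on treatment.

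**5. Timing.** Visit windows are ignored, and committee review and enrollment are taken as immediate.

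- Last regimen 1 patient, fastest case: regimen 2 opens on this patient's Day 36; its second patient starts at least 7 days after its first (5.3.2) and needs 35 more days to reach Day 36. 36 + 7 + 35 = Day 78.
- DLT window (7.2.2.2.3) closes on Day 36: 78 − 36 = 42 days earlier.
- Two cycles last 49 + 42 = 91 days, so Cycle 3 Day 1 is Day 92, and 92 − 78 = 14 days. Day 78 is Cycle 2 Day 29 (49 + 29), a dosing day, and the next dosing day is Day 92. Missing that one opportunity satisfies the 2-cycle condition.
- First regimen 1 patient: the others join only after this patient's Day 36 review and need 35 days themselves. 36 + 35 + 7 + 35 = Day 113, already past Day 92.

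The 2-cycle condition therefore binds only in a narrow window. The Grade 2 condition does not depend on the calendar.

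**The case against.** The strongest reply is that 7.2.1.2 is the specific and restrictive rule, while 7.2.2 is a general paragraph that waives nothing. A site must satisfy both. For the rise to 1600 mg this stands. A reader might infer that all 6 to 12 patients on regimens 1 and 2 (2 × 3 to 6) could reach 1600 mg without the patient-level conditions; the documents do not support that. The reply does not settle the 1200 mg step, which is either not allowed at all or allowed with no patient-level gate.

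Second, 7.2.2 is not unlimited. It applies to run-in patients only, needs a committee safety finding and has a dose ceiling. Re-dosing criteria are checked at each later visit, and the Steering Committee Charter, which is not among the documents, may say more. This stands in part: the re-dosing rules decide whether a patient may be dosed again, not whether the dose may rise.

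Third, 1200 mg is below the 1600 mg Q2W given in Arm A, and Section 3.2.5.1 reports similar safety across dose groups in an earlier study that included 1200 mg Q2W. This stands and limits the likely harm, although neither setting includes pembrolizumab.

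Two further inferences go too far. Footnote d of Table 4 ("If control achieved or ≤Grade 2, pembrolizumab and/or IFX-1 may be resumed") might look like another route to dosing with an ongoing Grade 2 event. It attaches to type 1 diabetes or Grade 3–4 hyperglycemia and to the Grade 3–4 rows of hypophysitis and hyperthyroidism, where 7.2.3 and general instruction 4 look for Grade 1 or baseline, so it is not relied on here. Nor does early escalation contaminate the DLT data, as step 5 of the working shows.

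**Conclusion.** The dosing rule is inconsistent as written, and the point is minor. The conflict is the step from 800 to 1200 mg Q2W: 7.2.2 permits it without any patient-level safety condition and 7.2.1.2 does not provide for it. If regimen 2 is the MTD, regimen 1 patients could go to 1200 mg under one section and get no increase under the other.

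The size is at most 3 to 6 patients, and only those still on treatment when regimen 2 is cleared. The documents give no rate of Grade 2 related AEs, so the share in actual conflict is unknown and could lie anywhere from none to all. The condition with practical effect is the one on AE history; two cycles will have been completed in most realistic calendars.

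DLT assessment and MTD determination are not affected. A reader might go on to infer an effect on the Simon design. No claim is made about it: the timing of the DLT window does not bear on response counting, and the documents do not say how an escalated patient would be counted toward the 10 who receive the RP2D.

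**What to change.** In Section 7.2.2, state that any intrapatient increase of IFX-1 requires at least 2 cycles received, no treatment-related AE of Grade 2 or higher, and consultation with the sponsor, as in 7.2.1.2. Name the three conditions rather than only pointing to 7.2.1.2, because that section's trigger (at least 3 regimen 3 patients) cannot sensibly govern a step to 1200 mg.

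In the same place, say whether the 800 to 1200 mg step is allowed. In the synopsis, add the two patient-level conditions to the 1600 mg rule.

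The cost is one sentence and one line in 7.2.2 and one clause in the synopsis, with no change to sample size or analysis. The downside is that slightly fewer run-in patients will qualify for escalation.
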